8.3 Concomitant Therapy

Medications used during the course of the study will be documented.

- 8.3.1 Prohibited Concomitant Therapy: The administration of concurrent medications intended to treat the primary cancer are not allowed during protocol therapy. This includes any chemotherapy, investigational agent, biologic agent or other anti-tumor agents. Radiation therapy is also prohibited.
- 8.3.2 Subjects should be strongly discouraged from taking any “alternative” or “naturopathic” medications since these agents may interfere with metabolism of study medications.

9.0 STUDY CALENDAR

Required Studies	Screening	Cycle 1-4 Day 1	Cycle 1-4 Day 8	Restaging ⁵	Cycle 5-16 day 1	Within 3 days prior to every 4 th cycle starting with cycle 17 while on umbralisib alone	End of treatment ⁷	Follow-up ⁶
Scheduling window (days)	-42 to -1 ⁹	+/- 3 days	+/- 2 days		+/- 3 days			
Physical								
History and Physical	X	X ¹			X ³	X	X	
Performance Status	X	X ¹			X ³	X	X	
Clinical Disease Assessment	X	X ¹			X ³	X	X ⁷	X
Adverse Event Assessment	X	X ¹			X ³	X	X	
Concomitant Medication Assessment	X	X			X	X	X	
Lab²								
TSH, T3, T4, LDH, ESR ²	X			X		X	X	
CBC with differential	X	X ¹	X	X	X	X	X	
Comprehensive metabolic panel	X	X ¹	X	X	X	X	X	
Serum pregnancy test ⁴	X ⁴							
Hepatitis B/C serology, direct and indirect coombs, CMV	X							
CMV surveillance by PCR ¹⁰		X ¹⁰			X ¹⁰	X ¹⁰	X ¹⁰	
Radiology								
EKG	X							
PET/CT ⁵	X			X			X ⁷	
CT ⁵				X				
Correlative Studies ⁸	X	X		X	X			

1. For Cycle 1 Day 1, pre-entry H&P, performance status, disease assessment and adverse event assessment may be used (these do not need to be repeated within 3 days) and labs done within 14 days of cycle 1 day 1 are acceptable.
2. LDH and ESR must be done within 14 days prior to study entry.
3. Between cycles 6-16 history, physical, performance status, and AE assessment by the investigator/sub-investigator may be performed every 2 cycles at investigator discretion.
4. Serum pregnancy test in women of childbearing potential should be performed with screening and repeated within 3 days of cycle 1 day 1.
5. FDG-PET-CT should be performed at baseline within 42 days prior to first dose of cycle 1. Diagnostic quality CT is not required at baseline for subjects who have CT measurable lesions from CT component of FDG-PET-CT. Follow up CT-scans should be performed after day 1 of cycle 3, 6, 9, 12 and 16, but prior to day 1 of the next cycle. PET-CT should be performed on the next imaging assessment for: 1) subjects meeting CR criteria by CT, 2) subjects meeting criteria for PR on 2 consecutive images, 3) subjects being removed from protocol for reasons other than progressive disease (including end of treatment), and 4) at the discretion of the investigator. For patients continuing on umbralisib for cycle 17 and beyond, imaging should be performed at the discretion of the investigator and upon clinical suspicion of progression/relapse.
6. Subjects continuing on umbralisib alone for cycle 17 and beyond should be seen in clinic every 4th cycle (Cycle 17, cycle 21, cycle 25 etc.).
7. There should be an end of treatment visit within 28 days after completion of therapy. For patients ending treatment on study for reasons other than progression, end of treatment imaging is strongly recommended within 28 days of completion of therapy. Imaging within this window can be recorded for a final response assessment. All subjects will be followed for survival and remission status while on treatment and up to 1 year after end of treatment visit.
8. Correlative studies will be carried out whenever possible and include PD1/PDL1/PDL2 expression, MRD (e.g. Adaptive Clonoseq or similar) and cytokine monitoring. This will include up to 10 unstained slides of diagnostic tissue block from most recent biopsy (additional biopsy not required for study entry), as well as whole blood for plasma (20 ml EDTA or equivalent) at baseline and after cycle 2, at end of 16 cycles or progression (whichever comes first), as well as any time point that a PET scan is being performed for response assessment
9. Testing can be performed within 42 days of cycle 1 day 1 unless specifically indicated above.
10. CMV screening by PCR within 3 days prior to cycles 4, 7, 10, 13 and 17, and then within 3 days prior to every 4th treatment cycle thereafter for all subjects receiving study treatment. A final CMV test by PCR should be done upon treatment discontinuation.

10.0 CRITERIA FOR EVALUATION AND ENDPOINT DEFINITIONS

Definitions of Disease, Criteria for Evaluation and Endpoint Definitions – response will be defined by standard NCI criteria (Lugano 2014) for lymphoid malignancies.

11.0 STATISTICAL CONSIDERATIONS

11.1 The primary objective of this study is to estimate the CR rate of this regimen. In a population of CHL patients who have failed after autologous transplant, the CR rate of single agent pembrolizumab is 16%². Targeted accrual is 20 subjects. If the assumed-true CR is 40%, we will have 88% power to observe a statistically significantly higher CR than the fixed rate of 16% with 20 subjects (at the one-sided significance level of 0.1). The 95% confidence interval (CI) by exact Clopper Pearson for the proposed 40% CR is from 19% to 64%, which will reasonable exclude a response rate of < 16%. With 20 subjects, CI will change to 27% to 73% with estimated CR 50%, and 36% to 81% with estimated CR 60%

11.2 Anticipated accrual: We anticipate accrual of 20 subjects over 2 years.

11.3 Descriptive summary statistics for continuous variables will include sample size, mean, standard deviation (SD), median, minimum and maximum for both baseline and post-baseline measurements (if applicable). Summary statistics for categorical variables will include sample size, frequency and percentages.

11.4 Estimated distribution of study population by gender and race and ethnicity:

Ethnic Category	Females	Males	Total
American Indian/Alaska Native			
Asian	1	1	2
Native Hawaiian or Other Pacific Islander	0	0	0
Black or African American	0	1	1
White	7	10	17
More than one race	0	0	0
Unknown or not reported	0	0	0
Racial Categories: Total of all subjects	8	12	20

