1.0 OBJECTIVES

- 1.1 Primary objective: To estimate the proportion of subjects with relapsed/refractory classical Hodgkin Lymphoma (CHL) who achieve a complete response (CR) with a regimen of umbralisib (oral, daily) and pembrolizumab (IV, day 1 of 21-day cycles).
- 1.2 Secondary objective: Overall response rate (ORR) and safety of this regimen.
- 1.3 Exploratory objective: 1-year overall survival (OS) and progression free survival (PFS), association of biomarkers with response.

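### Does quoting 88% power for a one-sided 10% test beside a two-sided 95% interval leave the comparison with 16% undecided?

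*Combined protocol and SAP*

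**What the plan says.** Section 11.1 opens with estimation: "The primary objective of this study is to estimate the CR rate of this regimen". It takes its benchmark from earlier single-agent data, where "the CR rate of single agent pembrolizumab is 16"%, and sets the size of the study: "Targeted accrual is 20 subjects". For a true CR rate of 40% it states that "we will have 88% power to observe a statistically significantly higher CR than the fixed rate of 16% with 20 subjects", and gives the level in the same sentence: "at the one-sided significance level of 0.1".

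The next sentence gives the exact Clopper-Pearson 95% interval for a 40% CR rate, 19% to 64%, and adds "which will reasonable exclude a response rate of < 16"%. The section then lists the intervals for estimated rates of 50% (27% to 73%) and 60% (36% to 81%).

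It gives no critical number of CRs and does not say how the interval relates to the test. Section 1.1 also states the primary objective as estimation, and neither section ties a go/no-go decision to the comparison with 16%.

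**The concern.** Two comparisons with the same 16% stand in consecutive sentences at different error levels. The test works at one-sided 10%. The lower limit of a two-sided 95% interval works at one-sided 2.5%. Power is given only for the first, so a reader who has just seen 88% may suppose that the interval will clear 16% about as often. The wording encourages this: 40% is the assumed true rate in the power sentence, but the interval that follows is the one for an observed 40%, that is 8 of 20.

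If the trial ended with 6 or 7 CRs, the test would be significant while the 95% interval contained 16%. With no rule saying which governs, the conclusion might seem open to choice after the data are seen, and the precision argument for 20 subjects might seem overstated.

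**Working it through.** **Inputs (all from section 11.1).** n = 20; p0 = 0.16; p1 = 0.40; one-sided level 0.10; 95% Clopper-Pearson interval. The text does not say that the interval is two-sided, but its limits match only the two-sided version. X is the number of CRs, binomial (20, p), with all 20 subjects counted.

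**1. The stated power.** The critical count is the smallest r with P(X ≥ r | 0.16) ≤ 0.10.

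- r = 5: 0.206, too large.
- r = 6: 0.087, so the test rejects from 6 of 20.
- Exact power: P(X ≥ 6 | 0.40) = 0.874.
- Arcsine approximation: Φ[2(arcsin√0.40 − arcsin√0.16)√20 − 1.282] = 0.877, which rounds to the stated 88%.

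The plan does not name the form of the test. The simple normal version, z = (x/20 − 0.16)/√(0.16 × 0.84/20), gives 1.098 at 5 CRs and 1.708 at 6, against a critical value of 1.282. The threshold is again 6.

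**2. The stated intervals.** For x CRs the lower limit is the 0.025 quantile of Beta(x, 21 − x), and the upper limit is the 0.975 quantile of Beta(x + 1, 20 − x).

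- 8/20: 19.1% to 63.9% (upper limit 63.95% before rounding); plan 19% to 64%.
- 10/20: 27.2% to 72.8%; plan 27% to 73%.
- 12/20: 36.1% to 80.9%; plan 36% to 81%.

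All three are reproduced. At 8/20 the lower limit is above 16%, so the sentence about exclusion is true of the interval it describes.

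**3. Test and interval count by count.**

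| CRs of 20 | One-sided exact p against 16% | 95% Clopper-Pearson | Test at 0.10 | Interval excludes 16% |
|---|---|---|---|---|
| 5 | 0.206 | 8.7% to 49.1% | no | no |
| 6 | 0.087 | 11.9% to 54.3% | yes | no |
| 7 | 0.030 | 15.4% to 59.2% | yes | no |
| 8 | 0.009 | 19.1% to 63.9% | yes | yes |

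**4. How often they differ.**

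- True 40%: P(X ≥ 6) − P(X ≥ 8) = 87.4% − 58.4% = 29.0%.
- True 35%: P(6 or 7) = 35.6%.
- True 16%: 8.7% − 0.9% = 7.8%.

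**5. Why they differ.** The lower limit of the two-sided 95% exact interval exceeds 16% only when the one-sided exact p is below 0.025. The p-values at 6 and 7 CRs, 0.087 and 0.030, lie between 0.025 and 0.10. Matching the level removes the gap: the one-sided 90% lower limit is 12.7% at 5/20 and 16.6% at 6/20, in agreement with the test.

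**The case for a change.** The strongest case for a change is this. The primary objective is estimation, and 95% is the only interval level the plan names, so that interval will stand beside the estimate in any report. About three times in ten, if the design assumption is exactly right, it will contain 16% although the test is significant. A sponsor could then stress whichever result suits. Writing down a count of at least 6 of 20, calling the 95% interval descriptive and stating the 58% would cost a few words and no subjects.

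The arithmetic of that case stands in full. So does the remark that the exclusion sentence, read as a forecast at a true rate of 40%, promises too much.

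The claim that the plan leaves the conclusion undetermined does not stand. No sentence makes the 95% interval the criterion for beating 16%. The only test of significance has its benchmark, sidedness and level stated, and these fix the threshold at 6 of 20. The 40% interval is followed by others at estimated rates of 50% and 60%, which marks the series as illustrations of precision at given estimates. The rival remedies, an 80% interval matched to the test or the 95% interval as criterion with 58% power, trade one error level against another. Neither corrects a figure in the plan.

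**Conclusion.** The concern does not call for a change. The plan's 88% agrees with the exact 87.4% at the level to which it is tied, the three intervals are reproduced, and the exclusion statement is true at 8 of 20. Followed as written, the plan yields a valid test (exact size 8.7%) and a valid 95% interval.

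What remains is missing detail: an unwritten critical count and an unstated relation between test and interval. An analyst can fill both from section 11.1 by reporting the one-sided test at 0.10 as the comparison with 16% and the 95% interval as the precision of the estimate, with both levels shown. At 6 or 7 CRs the report would say that 16% is exceeded at one-sided 10% but not at one-sided 2.5%, which is an accurate account of such data.

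Readers should not carry the 88% over to the interval: its probability of excluding 16% at a true 40% is 58.4%. These figures assume 20 counted subjects, an exact binomial test and a two-sided Clopper-Pearson interval. The threshold of 6 also holds under the simple normal test.

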12.0 STUDY MONITORING AND REPORTING PROCEDURES

12.1 Adverse Event Reporting

Reporting of AEs and SAEs should commence after first administration of either umbralisib or pembrolizumab, and should continue for up to 30 days after

last dose of study treatment (pembrolizumab or umbralisib, whichever is given last).

Complete and timely reporting of adverse events (AEs) is required to ensure the safety of subjects. Reporting requirements are determined by the characteristics of the adverse event including the *grade* (severity), the *relationship to the study therapy* (attribution), and the *prior experience* (expectedness) of the adverse event. The guidelines outlined in this section, as well as the specific direction on each report form must be followed. The NCI Common Terminology Criteria for Adverse Events v5.0 (CTCAE) will be used to classify and grade toxicities. The CTC can be found on the Cancer Therapy Evaluation Program (CTEP) homepage at https://ctep.cancer.gov/protocolDevelopment/electronic_applications/docs/CTC_AE_v5_Quick_Reference_8.5x11.pdf

12.2 Definitions and descriptions of terms used in adverse event reporting.

Adverse Event (AE)

An *adverse event (AE)* is defined as any unfavorable and unintended sign (including an abnormal laboratory finding), symptom, or disease temporally associated with the use of a medical treatment or procedure. The investigator should log AEs that are deemed to be clinically significant and assess their attribution to either or both of the study medications.

Serious Adverse Event or Adverse Drug Reaction

A *Serious Adverse Event (SAE)* or *Adverse Drug Reaction (ADR)* means any AE/ADR occurring at any dose that results in:

- Death;
- A life-threatening AE/ADR (i.e, the patient/subject was, in the view of the initial reporter/investigator, at immediate risk of death from the AE as it occurred. It does not refer to an AE that hypothetically might have caused death if more severe);
- Inpatient hospitalization or prolongation of existing hospitalization (i.e, hospitalization was required to treat or diagnose the AE/ADR: excludes hospitalization for unrelated reasons);
- A persistent or significant disability or incapacity (disability here means that there is a substantial disruption of a person's ability to conduct normal life functions);
- A congenital anomaly/birth defect;
- An important medical event (i.e., AEs/ADRs that might not be immediately life-threatening, or result in death or hospitalization might be considered serious when, based upon appropriate medical and scientific judgment, they might jeopardize the patient/subject or might require medical or surgical intervention to prevent one of the other serious outcomes listed above);

- Any suspected transmission via a medicinal product of an infectious agent.

Grade

Grade is defined as the severity of the adverse event. The CTCAE Version 5.0 must be used to determine the grade of the adverse event. If toxicity is not listed in the CTCAE use the following general criteria for grading.

- 0 – No adverse event or within normal limits
- 1 – Mild adverse event
- 2 – Moderate adverse event
- 3 – Severe adverse event
- 4 – Life-threatening or disabling adverse event
- 5 – Fatal adverse event

Attribution

Attribution is defined as the determination of whether an adverse event is related to a medical treatment or procedure. The investigator or authorized sub-investigator will assess attribution according to the following categories:

- *Unrelated*: the adverse event is *clearly NOT related* to therapy
- *Unlikely*: the adverse event is *doubtfully related* to therapy
- *Possible*: the adverse event *may be related* to therapy
- *Probable*: the adverse event is *likely related* to therapy
- *Definite*: the adverse event is *clearly related* to therapy

Unexpected Adverse Event

An *unexpected adverse event* is any adverse event that is not listed in the current Investigator's Brochure, package insert, protocol, or associated documents; or the specificity or severity of which is not consistent with these documents.

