8.0 DOSAGE MODIFICATION, DELAY, OR DISCONTINUATION

8.1 Dose modification of pembrolizumab

8.1.1 Withholding pembrolizumab: Adverse events (both non-serious and serious) associated with pembrolizumab exposure may represent an immunologic etiology. These adverse events may occur shortly after the first dose or several months after the last dose of treatment (see below). The use of corticosteroids should be considered for management of immune-related adverse events (irAEs). Please refer to prescriber

manual for further detail on dosing of corticosteroids for pembrolizumab-related toxicity. If the drug-related toxicity does not resolve to Grade 0-1 within 4 weeks after onset of toxicity, discontinuation is recommended. Pembrolizumab must be withheld for drug-related toxicities and severe or life-threatening AEs as per the below criteria (may resume upon recovery to grade 0 or 1 toxicity unless otherwise noted below).

- Hematological toxicity- Grade 4; Pembrolizumab should be held until resolved to Grade ≤ 3 .
- Colitis, any Grade- Grade 2-3; also administer high-dose systemic corticosteroids (followed by a taper).
- Hyperthyroidism- Grade 3; administer high-dose systemic corticosteroids (followed by a taper).
- Hypophysitis- Grade 2-4; administer high-dose systemic corticosteroids (followed by a taper).
- Nephritis- Grade 2; consider administration high-dose systemic corticosteroids (followed by a taper).
- Pneumonitis- Grade 1-2; administer high-dose systemic corticosteroids (followed by a taper). Pembrolizumab may be resumed after resolution.
- Hepatitis- Grade 2-3. Pembrolizumab should be held until resolution to Grade ≤ 1 . If the subject has baseline liver involvement and Grade 2 abnormalities at baseline, treatment may continue unless it worsens to Grade 3.
- Other treatment-related toxicity, severe or Grade 3; may require high-dose systemic corticosteroids (based on severity). Upon improvement to grade 0 or 1, initiate corticosteroid taper and continue to taper over at least 1 month. Restart pembrolizumab if the adverse reaction remains at grade 0 or 1 and steroid dose is ≤ 10 mg. Please refer to the FDA approved pembrolizumab prescribing information for more information.

8.1.2 Discontinuing Pembrolizumab: If any of the following criteria are met, pembrolizumab should be permanently discontinued

- Confirmed radiographic disease progression per the appropriate tumor evaluation criteria.

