12.3 Routine Reporting

Routine reporting is required for all grade adverse events. Routine reports include data after each cycle of therapy and 30 days after the last dose of study drugs, or until the patient receives an alternative anti-cancer therapy, whichever date comes first.

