12.4 Expedited Reporting –

SAE Reporting to TG Therapeutics

SAEs require expeditious handling and reporting to TG Therapeutics in order to comply with regulatory requirements. All SAEs (regardless of causality assessment) occurring on study or within 30 days of last study treatment should be immediately reported to TG Therapeutics at [contact] (copy

[contact] and [contact]) within 24 hours of the first knowledge of the event by physician member of the research team or research personnel on an SAE Form (MedWatch FORM FDA 3500 or equivalent) and followed until resolution (with autopsy report if applicable). Include the TG Therapeutics, Inc. tracking number (TGR-NTG-001) on the SAE report.

SAE Reporting to Regulatory Agencies

Sponsor-Investigator is responsible for reporting serious, unexpected, suspected adverse reactions (SUSARs) to the FDA in accordance with regulations under 21 CFR 312.32. Sponsor-Investigator is responsible for reporting unexpected fatal or life-threatening events associated with the use of the study drugs to the FDA within 7 calendar days after being notified of the event. Sponsor-Investigator will report other SUSARs to the FDA by a written safety report within 15 calendar days of notification. Other SAEs will be reported to the FDA on an annual basis.

The investigator must report SAEs and follow-up information to the responsible Institutional Review Board (IRB) according to the policies of the IRB.

The following are events of special interest, and will need to be reported within 2 business days of awareness by a member of the study team with exceptions as indicated below for reporting these events to TG Therapeutics within 24 hours of awareness:

Pregnancy, Abortion, Birth Defects/Congenital Anomalies

During the course of the study, all female subjects of childbearing potential must contact the treating investigator immediately if they suspect that they may be pregnant (a missed or late menstrual period should be reported to the treating investigator).

If an investigator suspects that a subject may be pregnant prior to administration of study drug(s), the study drug(s) must be withheld until the result of the pregnancy test is confirmed. If a pregnancy is confirmed, the patient must not receive any study drug(s), and must be discontinued from the study.

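### Adverse event collection closes 30 days after both drugs stop, so late immune-related events, which the protocol itself anticipates, can be missed from the safety results and the 7.5 count

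*Combined protocol and SAP*

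**What the plan says.** - **Collection window (12.1).** AE and SAE reporting begins at the first dose of either drug "and should continue for up to 30 days after" the final dose. The clock runs from the "last dose of study treatment (pembrolizumab or umbralisib, whichever is given last".
- **SAEs (12.4).** SAEs of any cause "occurring on study or within 30 days of last study treatment should be immediately reported". There is no cut-off at new therapy.
- **Routine AE reports (12.3).** These run to 30 days after the last dose, "or until the patient receives an alternative anti-cancer therapy, whichever date comes first".
- **Latency (8.1.1).** Of adverse events that may have an immunologic cause, the protocol says: "These adverse events may occur shortly after the first dose or several months after the last dose of treatment".
- **After treatment (9.0, footnote 7).** "There should be an end of treatment visit within 28 days after completion of therapy". Then: "All subjects will be followed for survival and remission status while on treatment and up to 1 year after end of treatment visit". In the calendar, the adverse event row is marked at end of treatment but not under Follow-up. The clinical disease assessment row is marked there.
- **Suspension rule (7.5).** The study is suspended if the lower one-sided 80% confidence limit for the rate of Grade 3-4 immune-related events not settling to Grade 2 or below within 72 hours exceeds 20%. The listed counts are 4 in 11 or fewer, 5 in 15 or fewer and 6 in 20 or fewer, with two of the first five subjects already counted. No observation window is given.
- **Objective (1.2).** Safety is a secondary objective, and 2.0 singles out immune-related toxicity for attention.

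**The concern.** The protocol expects that some immune-related toxicity may surface months after dosing ends, but its systematic collection closes at 30 days. Subjects remain under follow-up after that, yet nobody is asked to record toxicity.

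Two uses of the data are exposed: the reported immune-toxicity rate, and the 7.5 count, which can only include what the study team learns about. Under the present rules the error from uncollected events runs one way, towards a lower rate and a less likely suspension. This matters more than usual here because the rule has already triggered once, at 2 of the first 5 subjects, and its threshold was then raised from 10% to 20%.

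**Working it through.** **1. Timeline for a subject who has stopped both drugs**

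| Time after last dose of either drug | What is collected |
|---|---|
| To day 28 | End-of-treatment visit, the last scheduled AE assessment |
| To day 30 | AEs (12.1) and SAEs (12.1, 12.4); routine AE reports stop earlier if new therapy starts (12.3) |
| Up to 1 year after the end-of-treatment visit | Survival and remission only |
| Several months | Immune-type events still possible (8.1.1) |

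**2. Reproduce the 7.5 counts.** The exact (Clopper-Pearson) one-sided 80% lower limit for x events in n subjects is the 0.20 quantile of Beta(x, n - x + 1).

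- 4/11: 21.7%; 4/12: 19.8%
- 5/15: 21.3%; 5/16: 19.9%
- 6/20: 20.1%

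The listed counts follow from this limit. Wald and Wilson limits give different maxima for n (12, 17, 21 and 13, 17, 22).

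**3. One missed event at a boundary.** 3/11 gives 14.3%, 4/15 gives 15.7% and 5/20 gives 15.8%. All are below 20%, so a single uncollected event is enough to prevent suspension at that point.

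**4. Effect on the chance of suspension.** Inputs: start at 2 events in 5 subjects, with 15 subjects to come (7.5). Let p be the true rate of qualifying events and m the share missed. Both are assumed, because the documents give neither. Each further subject adds one counted event with probability q = p(1 - m). The listed counts are checked after every subject: suspend at 4 for n up to 11, at 5 for n = 12 to 15, and at 6 for n = 16 to 20.

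The first stage has a closed form, since two more events are needed among subjects 6 to 11: 1 - (1 - q)^6 - 6q(1 - q)^5.

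- p = 0.30, m = 0, so q = 0.30: 1 - 0.1176 - 0.3025 = 0.580
- p = 0.30, m = 0.20, so q = 0.24: 1 - 0.1927 - 0.3651 = 0.442

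Carrying the recursion on gives 0.695 and 0.540 by subject 15, and 0.789 and 0.627 by subject 20. The full range:

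| True rate | 0% missed | 10% missed | 20% missed | 30% missed |
|---|---|---|---|---|
| 20% | 49% | 42% | 35% | 28% |
| 30% | 79% | 72% | 63% | 53% |
| 40% | 94% | 90% | 83% | 74% |

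The model assumes independent subjects with a common rate. Section 7.5 counts subjects, so m is the share of further qualifying subjects whose only qualifying event falls outside the window. It also assumes that a late event, if collected, would be known in time to affect enrolment. The differences between columns are therefore upper limits on the effect on suspension.

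**The case against.** The case on the other side limits the point in several ways.

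- **Whichever drug ends later.** A reader might infer that every subject's late pembrolizumab events are lost. The documents do not support that. Umbralisib continues until progression or unacceptable toxicity (7.2) and may continue after pembrolizumab stops (7.4.3, 7.4.5). For those subjects the window stays open, so the gap concerns subjects off both drugs.
- **New therapy.** A reader might infer that SAE collection also ends when new therapy starts. It does not: that cut-off is in 12.3 only, and 12.4 keeps the full 30 days. Because 12.1 sets 30 days as a maximum, 12.3 differs from it without flatly contradicting it. The sections still need aligning.
- **Late events are not barred from 7.5.** The rule has no window, so a late event that the team hears of could be counted. Reporting of serious unexpected reactions to the FDA (12.4) and of unanticipated problems to the IRB (14.3) has no stated 30-day limit. These routes are not systematic collection, so the supported wording is that events can be missed.
- **Repeat events.** A subject who stopped because of a qualifying event is already counted, and a later one changes nothing under 7.5.
- **Simpler arithmetic.** A reader might compute 6 or more of 20 from a fresh binomial at 30% and obtain 58%, 46% and 34% with 0%, 10% and 20% missed. That ignores the two events already counted and the two earlier boundaries, and overstates the loss.
- **Longer collection has its own error.** Events caused by a subsequent therapy could enter the count.

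All of this narrows the point. None of it supplies planned AE collection after day 30 for subjects off both drugs.

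**Conclusion.** The point holds for subjects who have stopped both drugs. Their planned collection window is shorter than the latency that 8.1.1 states, and follow-up does not fill the gap, so the Grade 3-4 immune-related rate can be understated.

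The size cannot be derived from the documents. Under the assumed range, at a true rate of 30%, the chance of suspension falls by about 7, 16 or 26 percentage points from 79% when 10%, 20% or 30% of further qualifying events are missed. An event reported after accrual ends cannot change enrolment and affects only the safety estimate. The direction is firm and the magnitude is illustrative.

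**What to change.** 1. Keep the 30-day window for AEs in general, and reconcile 12.3 with 12.1 and 12.4 so that all three state the same end of collection.
2. For Grade 3 or higher immune-related AEs and related SAEs, extend collection beyond 30 days at the existing follow-up contacts, for a stated period consistent with 8.1.1. The 4 months after last dose already used for contraception (5.1 and Appendix 3) is one convenient choice. It should be described as a chosen period, because the documents do not tie it to immune-event latency.
3. Do not end this extended collection when new therapy starts. Record the start date of that therapy and the attribution of each event.
4. Add an AE check to the Follow-up column of the calendar in 9.0.
5. State in 7.5 that events collected this way count.

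The cost is a small amendment and a few extra CRF entries at contacts already planned. The downside is that attribution becomes harder once new therapy has begun. The change concerns data collection and counting only; no dose or treatment rule is altered.

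### Section 12.2 limits the adverse event log to events judged clinically significant, while 12.1 and 12.3 ask for complete, all-grade reporting, so low-grade events can be under-counted

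*Combined protocol and SAP*

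**What the plan says.** Four statements in the protocol bear on which AEs are recorded.

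- Section 12.1 sets the general standard: "Complete and timely reporting of adverse events (AEs) is required to ensure the safety of subjects".
- Section 12.2 defines an AE broadly: "any unfavorable and unintended sign (including an abnormal laboratory finding), symptom, or disease temporally associated with the use of a medical treatment or procedure". This definition carries no condition on clinical importance, and the grading scale in the same section starts its events at "1 – Mild adverse event".
- The sentence after that definition gives the logging instruction: "The investigator should log AEs that are deemed to be clinically significant and assess their attribution to either or both of the study medications".
- Section 12.3 then states: "Routine reporting is required for all grade adverse events". It adds no significance condition.

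Section 1.2 makes the results matter, because the secondary objective is "Overall response rate (ORR) and safety of this regimen". Section 11.3 provides only descriptive summaries, with frequencies and percentages for categorical variables, and gives no AE-specific analysis.

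**The concern.** The logging sentence in 12.2 serves no purpose unless it restricts what goes into the log. Read that way, an event can meet the protocol's own AE definition and have a CTCAE grade, yet be left out because the investigator judged it unimportant. Section 12.3 would require the same event to be reported. The protocol gives no criterion for the judgement, such as grade, symptoms or treatment action, and no order of precedence between the sections.

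The filter is also wider than a rule for laboratory findings alone. It covers symptoms and signs as well. Two investigators, or one investigator at two times, could log the same mild event differently, and both would be following 12.2. With 20 subjects and a purely descriptive safety summary, what is logged is the result. The risk is that the absolute frequency of low-grade AEs is understated.

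**Working it through.** No figure in the plan is derived from the logging rule, so there is none to reproduce. The check is a comparison of text, followed by a bound on how much is exposed.

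**Step 1: one event under each rule.** Take a Grade 1 asymptomatic laboratory change that the investigator considers unimportant.

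| Section | Treatment of this event |
|---|---|
| 12.2, definition | It is an AE; abnormal laboratory findings are included |
| 12.2, grading | It counts; Grade 1 is the lowest event grade |
| 12.2, logging sentence | It need not be logged |
| 12.1 | It belongs in a complete report |
| 12.3 | It must be reported; all grades are included |

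The logging sentence is the only one of the five that lets the event go.

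**Step 2: what lies outside the filter.** Section 12.4 covers "All SAEs (regardless of causality assessment) occurring on study or within 30 days of last study treatment", so serious AEs do not depend on 12.2. For transaminase changes of Grade 2-3, 8.1.1 holds pembrolizumab and the 8.2 table delays umbralisib, with an exception for subjects who have liver involvement and Grade 2 abnormalities at baseline. An event that interrupts both drugs is unlikely to be judged unimportant. What remains exposed is mainly Grade 1 events and asymptomatic laboratory changes.

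**Step 3: a ceiling on the laboratory part.** Inputs are the target accrual of 20 (11.1) and the pembrolizumab laboratory rates in Hodgkin lymphoma (3.1.1). These are 34% any grade and 2% Grade 3/4 for hypertransaminasemia, and 15% and 0.5% for creatinine increase.

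Expected subjects below Grade 3 = 20 × (any-grade rate − Grade 3/4 rate).

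- Transaminases: 20 × 0.34 = 6.8 any grade; 20 × (0.34 − 0.02) = 6.4 below Grade 3.
- Creatinine: 20 × 0.15 = 3.0 any grade; 20 × (0.15 − 0.005) = 2.9 below Grade 3.

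Both are upper limits on what discretion could remove. They apply single-agent rates to a combination and suppose that every event below Grade 3 could be dropped. They also pool Grade 1 with Grade 2, although Grade 2 transaminase changes normally trigger the holds in Step 2. Section 3.1.1 does not separate Grades 1 and 2, so the number truly at risk cannot be derived.

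**The case against.** The best defence is that significance and grade are different axes: 12.2 selects the events to log, and 12.3 then requires every grade of the selected events to be reported. The word *only* does not appear in 12.2, and 12.1 says that the directions on each report form must be followed, so the forms may settle the matter. This reading is possible, but the protocol does not state it. It sits badly with the AE definition and with complete reporting in 12.1. The forms are not part of the documents and cannot be assumed to resolve the conflict.

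Other parts of the defence stand, and they rule out stronger conclusions that a reader might draw.

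- **That the suspension rule in 7.5 is undermined.** The documents do not support this. That rule counts Grade 3-4 immune-related events that fail to improve to Grade 2 or lower within 72 hours, and such events are unlikely to be judged unimportant. Section 7.5 records that a Grade 3 ALT elevation was captured and counted towards the first suspension.
- **That the trial's rates could not be set beside those in 3.1.1.** For the laboratory rates this does not follow. Blood counts and chemistry are scheduled on day 1 of cycles 1-16 and day 8 of cycles 1-4, so matching figures can be computed from the laboratory values. No such comparison is planned in any case.
- **That the study calendar adds a second contradiction**, because footnote 3 says that "AE assessment by the investigator/sub-investigator may be performed every 2 cycles at investigator discretion". This relaxes only the investigator's assessment, between cycles 6 and 16. Blood counts, chemistry and review of concomitant medication continue each cycle. Section 12.3 asks for data after each cycle, not for an investigator assessment each cycle.
- **That open-label judgement biases a treatment comparison.** There is one arm, so the only issue is under-ascertainment of absolute rates.

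**Conclusion.** The conflict is real and lies in the wording. Section 12.2 applies an undefined, discretionary filter to all AE types, 12.1 and 12.3 do not, and no section takes precedence. If 12.2 is followed as written, the descriptive rates of low-grade AEs for the secondary safety objective can be too low.

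The size cannot be estimated from the documents. The ceilings above show that, at single-agent rates, nearly all expected transaminase and creatinine abnormalities fall below Grade 3. They do not show that any would be missed. Under-counting is possible, not demonstrated. It would matter most for mild symptomatic events, which, unlike laboratory changes, cannot be rebuilt from scheduled test results. Serious AEs and the primary endpoint are outside the filter, and Grade 3-4 immune-related events are largely protected by their clinical consequences. The sample size and the suspension boundaries do not change.

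The conclusion assumes that the logging sentence restricts the log, which is its natural meaning, and that no unseen form overrides it.

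**What to change.** Replace the logging sentence in 12.2 so that it agrees with 12.3. Suggested wording: *Log all AEs of any CTCAE v5.0 grade and record the attribution of each to either or both study drugs. Clinical significance, where assessed, is recorded in a separate field and does not determine whether an event is logged.*

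If a filter is wanted for laboratory findings alone, three changes are needed together:

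1. State an objective criterion in 12.2.
2. Amend 12.3 to carry the same criterion.
3. Add to section 11 a table of laboratory abnormalities by CTCAE grade, computed from the values already collected.

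The cost is an amendment to one or two sentences and a little more data entry. No new tests or visits are needed. For subjects already treated, laboratory abnormalities can be completed from existing results. Mild symptoms can be recovered only as far as the medical record allows, and the report should say so.
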